Randomized Clinical Trial of Exparel vs Pain Pump for Post-operative Pain Control after Total Shoulder Arthroplasty

INTRODUCTION

Routine anesthetic care for patients undergoing a Total Shoulder Arthroplasty (TSA) at our institution includes the implantation of a pain pump. A pain pump is used to allow pain control in the days after a TSA. Anecdotally patients complain of breakthrough pain the night after their surgery when the local anesthetic administered during surgery starts wearing off [Abdallah].

Exparel (Bupivacaine liposome injectable suspension), a sustained-release preparation of bupivacaine that is FDA approved for administration at the surgical site, may provide a lower-cost alternative to a pain pump, as it has the potential for activity up to 72 hours after surgery [Davidovitch, Golf, Haas]. Two prior randomized clinical controlled trials have compared Exparel to an intraoperative interscalene block and showed improved pain scores and less opioid consumption at 24 hours after surgery. There have been no studies comparing Exparel to a pain pump and evaluated the outcomes beyond 24 hours after surgery.

The primary objective of this study is to determine if Exparel leads to better pain scores at 24, 48 and 72 hours after TSA compared to a pain pump. Secondary objectives are (1) to determine if patients on Exparel use less narcotics and (2) have earlier return of functional use of the involved arm after surgery compared to the pain pump.

METHODS

Sample size:

Based on prior studies on anesthetics for TSA, the mean worst pain score in the 24 hours after surgery was 5.4, based on a 0 to 10 scale. To detect a change of 2 points, alpha of 0.05, beta of 0.80, a sample size of 51 subjects in each group will be required. To account for drop-outs, a total of 60 subjects in each arm will be enrolled.

Inclusion criteria

- Patients undergoing unilateral primary TSA or reverse TSA
- Indication for surgery is osteoarthritis, rotator cuff arthropathy or massive irreparable rotator cuff tears
- Surgery performed by the Principal Investigator ([name])
- Anesthesia administered by Co-Principal Investigator ([name])
- Willing and able to sign an Informed Consent

Exclusion criteria

- Indication for surgery is fracture
- Comorbid psychiatric diagnosis requiring therapy and/or medication except anxiety or depression
- Comorbid chronic pain syndrome (reflex sympathetic dystrophy, fibromyalgia)
- Has hepatic disease

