- On workers compensation/disability/litigation
- Known adverse reaction to medications to be administered

- On long-acting narcotic pain medication (including extended release narcotic pain medications and methadone)
- Home Oxygen requirement whether PRN or scheduled.
- Contralateral Phrenic Nerve paralysis / incompetence.
- BMI ≥ 50
-

Randomization will be a varied blocked randomization with blocks of 12, 15 and 18 using sealed envelopes

Treatment arms:

Control: Pain catheter based pain control. Subject will receive an interscalene block with Ropivacaine 0.5% (20cc), and then a pain pump attached in the PACU infusing at 4cc/hr. The patient will go home with that device until it runs out.

Interventional: Single shot Exparel 10cc (133mg) mixed with 10cc of 0.5% Bupivacaine

Both arms will receive the same multimodal analgesia medications preoperatively. Celebrex 400mg PO, Gabapentin 600mg PO, Tylenol 1 gram PO, unless contraindicated.

Variables collected

Pre-operative

Age

Sex

Race/Ethnicity

Educational Level

Height

Weight

Side of Arthroplasty

Current pain medication

Pain (NRS, 10 to 10)

ASES

SANE

Work status

Annual income

Days off work

In Hospital

ASA score

Local anesthesia start time

Local anesthesia end time

Operative time

Length of hospital stay

Cumulative MMEs consumed at 24, 48 and 72 hours

Worst pain in past 24 hours at 24, 48 and 72 hours post-op

Duration of sleep

Intraoperative complications

Postoperative complications

Pump failure (Yes/No) queried at 24, 48 and 72 hours

Catheter migration (Yes/No) queried at 24, 48 and 72 hours

Functionality of surgical arm at 24, 48 and 72 hours

Unable to use, Only light activity, Able to do some activities, Able to do most activities, Slight restrictions only, Normal

Six weeks post-operative

Current pain

ASES

SANE

Complications

Three months post-operative

Readmissions

Visits to the Emergency Room

Total costs for Index surgery and all readmissions and Emergency Room Visits

Date returned to work

Statistics:

Baseline data will be compared

ANCOVA or GEE to examine differences in worst pain scores over 24 hours over time between the two groups (among the three groups)

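### The only named events queried at 24, 48 and 72 hours are pump problems; events possible in either arm are collected without definition or a set query

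*Combined protocol and SAP*

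**What the plan says.** The In Hospital list under Variables collected contains two items with a Yes/No format and a stated query schedule: "Pump failure (Yes/No) queried at 24, 48 and 72 hours" and "Catheter migration (Yes/No) queried at 24, 48 and 72 hours". Under Treatment arms, only control patients have a device: they receive an interscalene block, "then a pain pump attached in the PACU infusing at 4cc/hr", and take the pump home until it is empty. The other arm is "Single shot Exparel 10cc (133mg) mixed with 10cc of 0.5% Bupivacaine", with no device.

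The remaining items timed at 24, 48 and 72 hours are opioid consumption, worst pain and arm function. Safety items not tied to one arm are "Intraoperative complications" and a postoperative counterpart in the In Hospital list, a complications item at six weeks, and readmissions and emergency visits at three months. None is defined, and no method of ascertainment is given. The two In Hospital complication items have no time point either.

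The exclusion criteria include "Home Oxygen requirement whether PRN or scheduled", "Contralateral Phrenic Nerve paralysis / incompetence" and "Has hepatic disease". The plan gives no reason for any of them.

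**The concern.** The home-oxygen and contralateral phrenic nerve exclusions suggest that the authors anticipated respiratory risk from the treatments. Yet no respiratory symptom is asked about in either arm, and neither is persistent numbness or weakness, or any symptom of local-anesthetic toxicity. Symptoms that resolve at home between 24 and 72 hours, and that nobody asks about, cannot be recovered at six weeks or three months.

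A second consequence touches a declared objective. Earlier functional use of the arm is a secondary objective, and function is scored at 24, 48 and 72 hours. The Introduction credits Exparel with possible activity up to 72 hours, so the whole scoring window may fall within its effect. A patient in the lowest category, who cannot use the arm, may have a persisting block, pain or post-surgical restriction. No collected item identifies a persisting block.

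**Working it through.** **1. Events set against arm and method of capture.**

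| Item | Possible in control | Possible in Exparel | Timing and method stated |
|---|---|---|---|
| Pump failure | yes | no | Yes/No at 24, 48, 72 h |
| Catheter migration | yes | no | Yes/No at 24, 48, 72 h |
| Intraoperative complications | yes | yes | the operation; no method |
| Postoperative complications | yes | yes | neither |
| Complications, six-week list | yes | yes | six weeks; no method |
| Readmissions, emergency visits | yes | yes | three months; no method |
| Respiratory, residual-block or toxicity symptom | not named | not named | none |

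The rows open to both arms are identical for both arms. What they lack is sensitivity. An intraoperative item precedes the 24 to 72 hour window. Readmissions and emergency visits miss any symptom that does not bring the patient back to hospital. The postoperative item sits in a list headed In Hospital, although control patients go home with the pump, and the plan does not say whether the item covers events after discharge.

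**2. What incomplete capture costs.** The plan gives no event rates, so the rates and capture fractions here are assumptions. The arm sizes come from the Sample size paragraph: 60 enrolled and 51 required.

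If a fraction c of cases with true rate p is captured, the probability of recording at least one among n patients is 1 − (1 − pc)^n.

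- Full capture, n = 60: p = 1% gives 1 − 0.99^60 = 45%; p = 2% gives 1 − 0.98^60 = 70%; p = 5% gives 1 − 0.95^60 = 95%.
- Full capture, n = 51: 40%, 64% and 93%.
- Half capture, n = 60, p = 2%: pc = 1%, so 70% falls to 45%.
- Two-fifths capture, n = 60, p = 5%: pc = 2%, so 95% falls to 70%.

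Zero recorded events in 60 gives a one-sided 95% upper bound of 1 − 0.05^(1/60) = 4.9% for the captured rate. If only half the cases are captured, the bound on the true rate is 4.9% / 0.5, about 9.7%. The documents do not allow the actual capture fraction to be estimated.

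**3. Function.** Scores fall at 24, 48 and 72 hours, and the Introduction's figure for Exparel is up to 72 hours. The pump runs until empty, but the plan gives no reservoir volume, so the duration of the control infusion is unknown. The ambiguity may therefore affect either arm.

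**The case against.** A reader might infer that the safety comparison is one-sided and biased toward Exparel, because controls are questioned about problems and Exparel patients are not. The documents do not support this, for three reasons.

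- The general complication items, readmissions and emergency visits are not restricted to one arm. A respiratory or drug event could be recorded there for any patient.
- No safety comparison is planned. The objectives are pain, narcotic use and arm function, and the Statistics section covers baseline data and worst pain only.
- A spurious excess in controls would require pump and catheter events to be pooled into a complication rate. The plan lists them as separate variables and nowhere says they will be pooled.

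Collecting device items only where there is a device is also reasonable. A failed pump means treatment was not delivered, which helps to interpret control-arm pain. That stands.

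The reading of the exclusions is an inference. It is fairly strong for home oxygen and contralateral phrenic nerve paralysis, and weak for hepatic disease. Only the control arm is explicitly given an interscalene block, and the route of the Exparel injection is not stated, so the respiratory concern cannot be assigned to Exparel in particular.

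Finally, a block that limits use of the arm is arguably part of functional return, whatever the mechanism. That stands for the estimate: the comparison of function scores remains valid. The point concerns explaining a difference or its absence.

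**Conclusion.** The point holds as one of insensitive capture. The only named events with a scheduled query are control-arm device problems, and events that both arms could have lack definitions and an ascertainment method. Capture is symmetric, no bias toward Exparel is shown, and the planned pain analysis is unaffected.

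The size depends on capture fractions that the plan does not reveal. Under the illustrative assumptions, halving capture lowers the chance of seeing a 2% event at least once in an arm of 60 from 70% to 45%. This assumes independent patients and no drop-out. The calculation shows scale only and does not estimate what this trial would miss.

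Severity is low. The change is still worth making before enrolment, because unasked 24 to 72 hour symptoms are lost for good and the function score would be easier to interpret.

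**What to change.** At the existing 24, 48 and 72 hour data points, ask both arms the same Yes/No questions, in the same words:

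- new shortness of breath or new need for oxygen;
- persistent numbness or weakness of the arm or hand;
- symptoms of local-anesthetic toxicity, from a short written list;
- an unplanned call or visit for any of these.

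State in the variables list what counts as a complication, how it is ascertained, and whether the In Hospital item covers events after discharge. Add to Statistics that the common list and complications will be tabulated by arm, descriptively and without a hypothesis test. Report pump failure and catheter migration separately, as control-arm device or treatment-delivery events. Show the numbness and weakness answers beside the function scores as context, not as an adjustment.

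The cost is a few questions at contacts already planned and two or three sentences of text. No added visits are needed. The downside is that more minor symptoms will be recorded in both arms.
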